Tube 4 is a 6 ml siliconized orange-green stopper tube with serum separator. This contains no anticoagulants and is submitted to the field center lipid laboratory for baseline lipoprotein profile. This is centrifuged at 4°C at 3000 g x 10 min and 4-0.5 ml aliquots are frozen at -80°C before analysis.

4. Description of blood collection tubes for endpoint package

Tube 1 is a 10 ml siliconized yellow/black stopper tube. This tube contains thrombin so that the blood clots to form serum in 5 minutes. Aliquots are coded red. This serum is used for the lipid profile and apoproteins.

Tube 2 is also a 10 ml yellow/black stopper tube. It is processed the same as Tube 1 and is used for aliquots of serum for later studies.

Tube 3 is a 4.5 ml blue-topper tube containing 0.5 ml of 3.8% sodium citrate. It is crucial that this tube remain at room temperature. After centrifugation, plasma is aliquoted into green-coded aliquots. The plasma will be used for Factor VII coagulation assay.

Tube 4 is also a 4.5 ml blue-stopper tube identical to Tube 3. It is different in the way it is processed. Instead of room temperature, this tube must be placed on ice after filling. Plasma from this tube is aliquoted into blue-coated aliquots and will be used for fibrinogen assay and PAI-1 assay.

Tube 5 is a 7.0 ml purple stopper tube. This tube requires mixing after filling and placement on ice. After centrifugation, plasma is aliquotted into yellow-coded cryovials (0.5 ml). The plasma will be used for ancillary and supplemental studies.

Each draw tube is assigned a color-coated aliquot system. There is one type of aliquot used: 0.5 ml cryovials. The cryovials have colored caps.

5. Priority of tubes

A total of 25.5 ml of blood will be drawn from each participant for each baseline package. The tubes are drawn in the following order: Serum 6 ml - orange/red top, EDTA plasma 3.5 ml - purple top, EDTA plasma 10.0 ml - purple top, serum 6 ml - orange/red top. All four tubes are required, as they assess inclusion/ exclusion criteria.

The tubes are numbered 1-4 and arranged on the rack in order of draw. Samples from the four tubes are used in approximately eight different biochemical and hematological assays. The buffy-coated aliquots (three) obtained from baseline are amber/brown cryovials, approximately 0.5 ml in each cryovial.

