A total of approximately 35 ml will be drawn from each participant in five tubes at each endpoint package. The tubes are drawn in the following order: Serum 10 ml - yellow/black top, serum 10 ml - yellow/black top, citrate plasma 4.5 ml - room temperature blue top, citrate plasma 4.5 ml - 4°C - blue top, and EDTA plasma 7.0 ml - 4°C. Tubes #1, 3, and 4 are of absolute priority and should be collected at each endpoint package, at the minimum.

The tubes are numbered 1-5 and arranged on the rack in order of draw (see diagram in this section). Samples from the five tubes are used in approximately 13 different biochemical and hematological assays.

6. Aliquot tube rack: Labeling and set up

Each participant will have two aliquot racks set up to correspond with the blood collection tube rack. Rack set up is completed the previous day. All tubes and vials are labeled and arranged appropriately (see diagram in this section). Aliquot assignments:

Polypropylene

Tube	Cryovials	Color Code
serum 10 ml	7 (0.5 ml)	red
serum 10 ml	7 (0.5 ml)	red
citrate 4.5 ml	4 (0.5 ml)	green
citrate 4.5 ml	4 (0.5 ml)	blue
EDTA plasma 7.0 ml	6 (0.5 ml)	lavender
TOTALS	28	

Each field center will be provided with a PC-based computer program to allow the inventory of aliquots stored at each field center to be tracked. Each field center will be responsible for the accurate maintenance of the inventory.

7. Forms

a. Purpose:

The purpose of the blood collection form is to facilitate the collection of plasma and serum samples from participants. This collection must be done in a rapid and efficient manner, with maximum protection for the participant. In addition, the process must facilitate the monitoring of phlebotomy and other quality assurance parameters as well.

Note: All forms are to be completed in ink.

b. Description:

There are two parts of the Phlebotomy Processing Form associated with blood drawing. The top half is the participant/phlebotomy question about fasting status. If the person has eaten less than eight hours earlier, he/she should be rescheduled on an alternate day, within three days of the initially scheduled date.

The bottom half deals with phlebotomy and processing of samples.

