Blood drawing is standardized for the sitting position. The venipuncture performed with the 21-gauge butterfly needle with 12 inches of plastic tubing between the venipuncture site and the blood collection tubes. The butterfly is a small, thin-walled needle which minimizes trauma to the skin and vein. The use of 12 inches of tube allows tubes to be changed without any movement of the needle in the vein. If the participant is concerned about the venipuncture, he/she may be reassured to know that such care is taken. The participant should be given enough time to feel comfortable both before and after the blood collection. In many cases, the most memorable part of the experience for the participant will be the contact with the person who draws the blood and their general attitude and competence. If the participant is nervous or excited, the technician briefly describes the procedure; e.g., "I am going to be drawing about 2 tablespoons of blood. This blood will be used for tests for lipids and cholesterol and blood clotting factors."

HANDLING PARTICIPANTS WHO ARE EXTREMELY APPREHENSIVE ABOUT HAVING BLOOD DRAWN.

Do not under any circumstances force a participant to have blood drawn. It may help to explain to the participant that the blood drawing is designed to be as nearly painless as possible. It is sometimes best to let the participant go on with another part of the examination. It may also be helpful to have the participant relax in the blood drawing chair just so the phlebotomist can check the veins in the participant's arms, without actually drawing blood.

6. Venipuncture procedure: Wear Latex gloves and lab coat

a) Arrange draw tubes in order of draw on the table top within easy reach. Assemble butterfly apparatus and vacutainer holders, gauze, and alcohol prep prior to tourniquet application.

b) Apply tourniquet to either arm.

- c) Examine participant's arms for the best site for venipuncture. Release tourniquet.
- d) Cleanse venipuncture site. Prepare area by wiping with alcohol swab in a circular motion from center to periphery. Allow area to dry.
- e) Reapply tourniquet and start timer.
- f) Grasp the participant's arms firmly using your thumb to draw the skin taut. This anchors the vein. The thumb should be one or two inches below the venipuncture site.
- g) With the needle bevel upward, enter the vein with a smooth continuous motion.

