(4) Paragraphs (d)(2) Engineering and Work Practice Controls, (d)(3) Personal Protective Equipment, (d)(4) Housekeeping, (e) HIV and HBV Research Laboratories and Production Facilities, (f) Hepatitis B Vaccination and Post-Exposure Evaluation and

Follow-up, and (g) (1) Labels and Signs, shall take effect July 8, 1992.

[FR Doc. 91-23866 Filed 12-2-91; 8:45 am]
BILLING CODE 4810-26-M

DELTA

Materials for center to have at time of training:

6/7/93

For safety

1. Institutional OSHA training policy, institutional procedures
2. Appropriate safety supplies for a phlebotomy station. OSHA acceptable personal protective equipment, appropriate disposal units for sharps and regulated medical waste, supplies for cleaning spills, etc.)

For Cholestech operation

1. Cholestech instrument, printer, paper, Optic check cassette, manual.
Materials for fingerstick blood draw (lancets, alcohol swabs, etc.)
Practice cassettes
2. Copy of procedure (supplied by [name])

For Baseline samples.

1. Phlebotomy supplies for drawing 4 Vacutainers - Vacutainer adapter and Vacutainers.
Vacutainers: 2 6-mL SST tubes (Becton Dickinson 367784)
1 3-ml lavender top (EDTA) (Becton-Dickinson 367661)
1 10 ml lavender top (EDTA) (Becton-Dickinson 6457)
2. Clinical centrifuge, transfer pipets, supplies. (Are also needed for endpoint samples. See attachments describing supplies for endpoint samples)
3. 2 Amber cryovials (0.5 ml) for buffy coats (e.g. Sarstedt 72.730.008)

DELTA

Materials for center to have at time of training (cont):
6/7/93

For endpoint samples

1. Blood collection tray - Supplies for drawing 5 Vacutainers. (See Chapter 10, p. 11, attached - Blood Collection Rack and Blood collection tray checklist)
Vacutainers: 2 9.5 mL SST (Becton-Dickinson 6510)
 2 4.5 ml blue top (citrate) (Becton-Dickinson 6418)
 1 10 ml lavender top (EDTA) (Becton-Dickinson 6457)
2. Equipment and supplies for sample processing and aliquoting including:
 - a. Two centrifuges (one refrigerated and one room temperature) with holders for Vacutainers and capable of at least 1500xg (preferably 3000xg).
 - b. 500 ul MLA pipet
 - c. Other supplies and equipment as listed from Chapter 10 (attached)
3. Supplies for archiving and shipping samples

For each subject endpoint sample

- 28 0.5 ml cryovials (Sarstedt #72.730.003) without caps
- 14 red caps - Sarstedt #65.716.003
- 4 green caps - Sarstedt #65.716.005
- 4 blue caps - Sarstedt #65.716.001
- 6 lavender caps - Sarstedt #65.716.008

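### A thrombin-containing serum tube is filled immediately before the Factor VII citrate tube, and before the fibrinogen/PAI-1 citrate tube, through one needle and tubing set with no discard

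*Protocol*

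**What the plan says.** Chapter 8, II.B.4 describes the five endpoint tubes. Of tube 1, the serum tube for lipids and apoproteins, it says "This tube contains thrombin so that the blood clots to form serum in 5 minutes". For the second serum tube it says "Tube 2 is also a 10 ml yellow/black stopper tube. It is processed the same as Tube 1". Tube 3 is citrate kept at room temperature: "The plasma will be used for Factor VII coagulation assay". Tube 4 is citrate placed on ice, and its plasma "will be used for fibrinogen assay and PAI-1 assay". Tube 5 is EDTA.

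II.B.5 (Priority of tubes) sets the sequence: "The tubes are drawn in the following order: Serum 10 ml - yellow/black top, serum 10 ml - yellow/black top, citrate plasma", followed by the iced citrate tube and the EDTA tube. It adds "The tubes are numbered 1-5 and arranged on the rack in order of draw (see diagram in this section". It also names tubes 1, 3 and 4 as the minimum set to be collected at every endpoint draw.

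II.B.7.d.5 prescribes one 21-gauge butterfly with tubing and explains: "The use of 12 inches of tube allows tubes to be changed without any movement of the needle in the vein". The venipuncture steps in II.B.7.d.6 have each stopper pierced in turn by the same holder needle, with a shut-off valve that stops flow between tubes.

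Two other places describe the tubes differently. Figure 2 lists the endpoint tubes as yellow/black, blue, blue, purple, yellow/black. The list of materials to have at training asks for "2 9.5 mL SST (Becton-Dickinson 6510") and does not mention thrombin.

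**The concern.** Section 1.0.3 names fibrinogen, Factor VII and PAI-1 as the primary hemostatic endpoints, and all three are measured on the citrate tubes. Two of them are read by clotting: fibrinogen by the Clauss clot-rate method (VI.E.1) and Factor VII by a one-stage clot-rate assay (VI.E.2). The tube ahead of them holds an additive whose stated purpose is to make blood clot quickly. Any residue left on the stopper-piercing needle after that tube goes into a sample that has to stay unclotted.

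The protocol takes trouble over this same sample elsewhere. II.B.4 treats room temperature as essential for the Factor VII tube, and VI.E.2 asks for quick thawing and immediate assay so that Factor VII is not activated beforehand. The draw order works against that care, and it can be changed cheaply. At stake is the measurement quality of Factor VII and, to a lesser degree, fibrinogen.

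**Working it through.** The protocol states no figure on this point, so the check is to trace the tubes through the sections.

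1. **Additive.** II.B.4 puts thrombin in tube 1 and gives tube 2 the same stopper and processing.
2. **Order.** II.B.5 gives serum, serum, citrate (room temperature), citrate (4°C), EDTA. The tube numbers in II.B.7.d.7, II.B.7.d.11, III.C, III.D and III.E agree with it. Tube 3 (Factor VII) therefore directly follows a thrombin tube. Tube 4 (fibrinogen, PAI-1) follows after a further 4.5 ml tube has been filled through the same needle.
3. **Path.** II.B.7.d.5 and d.6 describe a single needle and tubing set. No discard, flush or needle change appears between the serum and citrate tubes. The valve stops flow but does not clear residue.
4. **Alternative order.** In Figure 2's sequence only one thrombin tube precedes the citrate tubes, but it still comes directly before the room-temperature citrate tube. The exposure of the Factor VII tube is the same under either sequence.
5. **Detection.** The assay controls in VI.E are control plasmas that never pass through a participant's needle. The longitudinal volunteers in VII.E are drawn in the same way as participants, so they share the exposure. The re-analysis of outliers in VII.C retests the sample already drawn. The plasma assessment in III.E records visible clotting, not a partial effect.
6. **Number of draws.** 4 endpoint draws per diet × 3 diets = 12 per participant. With the 96 participants assumed in Table 1 and no dropout, 12 × 96 = 1,152 draws use this order.
7. **Size.** The protocol gives neither a thrombin concentration nor a residual volume, so the size of any effect cannot be computed.

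**The case against.** **The mechanism is inferred.** The protocol nowhere discusses additive carry-over, and the only Factor VII activation hazard it names is cold. This stands as a limit on the claim. What the text does establish is a clotting additive immediately upstream of a clot-based assay, with nothing in between to clear it. That supports a possibility, not a demonstrated effect.

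**Some protection exists.** II.B.7.d.6 keeps the tube below the puncture site and has the valve re-cover the needle point between tubes, and III.E would flag overt clotting. These lower the risk. None of them clears the needle or reveals a partial effect.

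**A reader might infer a large variance inflation.** One could assume a carry-over SD of 1% to 5% and set it against the fibrinogen monthly CV of 3.09% in VI.E.1: 1²/3.09² to 5²/3.09², about 10% to 262%. The same assumption against the blind-duplicate technical error of 7.4% in the same paragraph gives 1²/7.4² to 5²/7.4², about 2% to 46%. The SD has no source, the answer depends on the denominator, and biological variation is left out. The documents support no such figure.

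**A reader might infer bias between diets.** They do not support this either. Every participant eats all three diets and one draw order applies throughout, so a constant additive shift cancels in within-person comparisons.

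**A reader might infer that some centers use thrombin tubes and others do not.** The training list is a single list for all centers. It shows an inconsistency in the document, not a difference in practice.

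**A reader might treat the three endpoints as equally exposed.** Only the Factor VII tube directly follows a thrombin tube. PAI-1 is measured by ELISA (VI.E.3), and nothing in the protocol shows that trace thrombin alters it.

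**Conclusion.** The point holds in a limited form. As written, the endpoint draw fills a thrombin tube immediately before the Factor VII sample and ahead of the fibrinogen and PAI-1 sample, through one uncleared needle and tubing set. Carry-over is possible, mainly into the Factor VII tube and less into the fibrinogen tube. For PAI-1 no effect is shown. The size is unknown and should not be put as a number. The expected consequence is noise, or a shift common to all diet periods, that the planned quality control would not detect.

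This rests on II.B.4 being right that the serum tubes contain thrombin. The training list and the 9.5 ml serum tubes in III.I leave the tube type unsettled. If no thrombin tube is used, II.B.4 is the error and the carry-over concern disappears. The inconsistency in tube type and tube order needs correcting in either case.

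**What to change.** - In II.B.5, set the endpoint order as: a small no-additive discard to clear the 12-inch tubing, citrate at room temperature, citrate on ice, thrombin serum for lipids, then the second serum tube and the EDTA tube. The lipid tube becomes the third collected tube and stays in the absolute-priority set, which would then be tubes 1, 2 and 3.
- Carry the new numbering through II.B.4, II.B.7.d, III.C to III.E and III.I.
- Make Figure 2 agree with II.B.5.
- Name one serum tube type and volume in II.B.4, III.I and the training materials list. If that tube contains no thrombin, correct II.B.4 instead; the reordering is then not needed on this ground.

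The cost is a few ml of discarded blood at each of the 12 endpoint draws per participant, plus relabelled racks and label sheets. The present serum-first order needs no discard, because the serum tubes already clear the tubing; the added discard is the price of the change.
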